4.3.2.2. Average Daily Number of Micturitions

Average daily number of micturitions is defined as the total number of times a subject checked “Urinated in toilet” or recorded non-zero urine volume in a completed bladder diary day within the visit window divided by the number of days the Bladder Diary is filled out. Subjects may have more than one bladder diary filled out on the same day and all the micturitions will be summed together. The denominator used for calculating the average number will only count the days in which there is a completed bladder diary day within the visit window.

4.3.2.3. Average Daily Number of UI Episodes

Average daily number of UI episodes is calculated as the total number of UI episodes recorded on a completed diary day within the visit window divided by the number of days the Bladder Diary is filled out. A UI episode is defined as when a subject answered “Yes” to the question “Accidental urine leakage” or indicates any reason for leakage on the bladder diary eCRF.

Subjects may have more than one bladder diary filled out on the same day and all the UI episodes will be summed together. The denominator used for calculating the average number will only count the days in which there is at least one completed bladder diary day within the visit window.

4.3.2.4. Average Daily Number of Urgency Episodes

Average daily number of urgency episodes is calculated as the total number of urgency episodes recorded on a completed diary day within the visit window divided by the number of days the Bladder Diary is filled out. An urgency episode is defined as when a subject answered “Yes” to the question “Need to urinate immediately” on the bladder diary eCRF. Subjects may have more than one bladder diary filled out on the same day and all the urgency episodes will be summed together. The denominator used for calculating the average number will only count the days in which there is at least one completed bladder diary day within the visit window.

4.3.2.5. Proportion of Subjects Achieving $\geq 50\%$, $\geq 75\%$, and 100% Reduction from Baseline at Week 12 in UUI Episodes per Day

Proportion of subjects achieving x% reduction from baseline is defined as: - (Average daily number of UUI episodes at Week n – UUI at Baseline) / UUI at Baseline * 100%. This is defined when both baseline and post-baseline average daily number of UUI episodes are non-missing. For responder analyses, missing reduction from baseline will be considered non-responders for the visit in question.

4.3.2.6. Average Volume Voided per Micturition

A subject is expected to fill out the volume voided for one 24-hour period during the 3-day diary collection window. The average volume voided per micturition is calculated as the arithmetic mean of all voids for which a subject has recorded a positive volume, even if volume voided is filled out for more than one 24-hour period.

4.3.2.7. Average Daily Number of Nighttime Voids

Average daily number of nighttime voids is defined as the total number of times a subject checked “Urinated in toilet” or recorded non-zero urine volume in a completed bladder diary day within the visit window between the hours of 11:00 PM and 6:00 AM the following day, divided by the number of days the Bladder Diary is filled out. Subjects may have more than one bladder diary filled out on the same day and all the nighttime voids will be summed together. The denominator used for calculating the average number will only count the days in which there is at least one completed bladder diary day within the visit window.

4.3.2.8. Proportion of Subjects Achieving $\geq 50\%$ and 100% Reduction from baseline in Number of Average Daily UI Episodes

Proportion of subjects achieving x% reduction from baseline is defined as: - (Average daily number of UI episodes at Week n – UI at Baseline) / UI at Baseline * 100%. This is defined when both baseline and post-baseline average daily number of UI episodes are non-missing.

For responder analyses, missing reduction from baseline will be considered non-responders for the visit in question.

4.3.3. Questionnaires Data and Scoring

4.3.3.1. Total Summary Score from I-QOL

I-QOL is a validated, disease-specific quality of life questionnaire designed to measure the impact of urinary incontinence on patients' lives. It contains 22 items. The response options and values for each item are:

- Extremely (value = 1)
- Quite a bit (value = 2)
- Moderately (value = 3)
- A little (value = 4)
- Not at all (value = 5)

A total summary score is calculated based on the 22 items; additionally, three domain scores (Avoidance and Limiting Behavior, Psychosocial Impact, and Social Embarrassment) can be calculated based on responses to items corresponding to each respective domain. The score will only be derived when at least 50% of the items are completed: i.e. ≥ 11 items are completed at one visit [1]. The three domains will be considered missing if the total score is missing. The three domains include the following items:

Table 5: I-QOL Scoring

Domain	Items	Lowest Possible Scores	Possible Range
Total Summary Score	1 to 22	22	88
Avoidance and Limiting Behavior	1, 2, 3, 4, 10, 11, 13, 20	8	32
Psychosocial Impact	5, 6, 7, 9, 15, 16, 17, 21, 22	9	36
Social Embarrassment	8, 12, 14, 18, 19	5	20

The total score and each domain score are based on the transformation of the raw score to a 0 to 100 scale using the formula below:

$$= \frac{\text{sum of the items} - \text{lowest possible score}}{\text{possible raw score range}} \times 100$$

The higher score corresponds to a better quality of life.

Subjects who had at least a 10-point increase of I-QOL total summary score from baseline to post-baseline visits are considered responders who achieved the minimally important difference (MID). Subjects who had an increase less than 10 points at any post-baseline or change from baseline is missing are considered non-responders.

4.3.3.2. OAB-q Scores

The OAB-q was developed to assess symptom bother and the impact of OAB on health-related quality of life (HRQL). It contains 33 items and the response options and values for each item are:

- Not at all / None of the time (value = 1)
- A little bit / A little of the time (value = 2)
- Somewhat / Some of the time (value = 3)
- Quite a bit / A good bit of the time (value = 4)
- A great deal / Most of the time (value = 5)
- A very great deal / All the time (value = 6).

The instrument yields a HRQL total score and four subscales as listed in the table below:

Table 6: OAB-q Scoring

Scale	Items	Lowest, Highest Possible Scores	Possible Range
Total HRQL	9 to 33	25, 150	125
Symptom Bother	1 to 8	8, 48	40
Coping	9, 11, 16, 21, 22, 26, 32, 33	8, 48	40
Concern	12, 13, 14, 19, 23, 25, 29	7, 42	35
Sleep	10, 15, 24, 17, 30	5, 30	25
Social Interaction	18, 20, 27, 28, 31	5, 30	25

For the Symptom Bother Score, the transformed score is:

$$= \frac{\text{sum of the items} - \text{lowest possible score}}{\text{possible raw score range}} \times 100$$

The higher score corresponds to a larger bother.

For Coping, Concern, Sleep, Social Interaction, and Total HRQL scores, the score is:

$$= \frac{\text{highest possible score} - \text{sum of the items}}{\text{possible raw score range}} \times 100$$

The higher score corresponds to a higher quality of life.

If < 50% of the scale items are missing, the scale will be retained with the mean scale of the items present used to impute a score for the missing items. If $\geq 50\%$ of the items are missing, no scale score will be calculated, the subscale score should be considered missing [2].

4.3.3.3. PGI-C Scale Score

The PGI scale in this study is an OAB-specific quality of life questionnaire. The tool was designed to assess the impact (and improvement) of urinary incontinence on activities of daily living, wellbeing, and function. The eCRF collects PGI severity, control, frequency, leakage, as well as change. All PGI scales are ordinal assessments going from lower impact of disease to highest impact of disease. PGI-Severity ranges from 1 to 4, PGI-Control, PGI-Frequency, PGI-Leakage range from 1 to 5. PGI-Change ranges from 1 to 7. These questions will be displayed as categorical variables with count and percent for each category at Week 12. Also, PGI-Change will be analyzed as a dichotomous responder variable. Subjects who answer “Much better” or “Moderately better” will be considered responders, while all other answers and missing values will be considered non-responders.

4.3.4. Study Day and Duration

Study day is relative to the start date of the double-blind treatment. This is used to describe the relative time of an event or assessment that happened during the study. The first day of the study is defined as the day a subject receives either URO-902 (24 or 48 mg) or placebo. There is no study Day 0 defined.

- For an event or assessment that occurred on or after the study treatment: Study day = Date of event or examination – date of study treatment + 1
- For an event or assessment that occurred prior to the study treatment: Study day = Date of event or examination – date of study treatment

A duration between any two dates (such as AE duration) expressed in days will be calculated using the following conventions: Duration = later date – earlier date + 1.

4.3.5. Baseline and Change from Baseline

In general, the last recorded value prior to the study treatment will serve as the baseline measurement for the safety endpoints such as lab, vital signs, and ECGs. For numeric result, the mean of the multiple values will be used as baseline if multiple measurements are collected on the same baseline day without the time or “repeat” status to differentiate the records. For categorical results, the record with the later sequence number or collection time will be used if multiple measurements are collected on the same baseline day. For the bladder diary data, the 3

diary days collected during the screening and randomization period and closest to the treatment administration is considered baseline. All 3 diary days are required for the change from baseline derivation. For the questionnaires, the baseline is the data collected on the Day 1 Visit prior to treatment.

Change from baseline will be calculated as the post-baseline value minus the baseline value. Percentage change from baseline will be calculated as the change from baseline divided by the baseline value, multiplied by 100. If either the baseline or post-baseline value is missing, then change from baseline and percentage change from baseline will be set to missing.

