4.2.3. Premature Withdrawal and Missing Data

If any missing data are present in diary data for any reasons, no imputation will be applied to derive responder. No explicit missing data imputation will be performed for change from baseline since a mixed model for repeated measures (MMRM) will be applied to change from baseline analysis. For responder analyses, subjects with missing assessments will be considered non-responders. Missing items from the questionnaires will be handled according to the respective measure instructions as described in [Section 4.3.3](#).

In general, missing safety data will not be imputed and only observed values will be analyzed.

If the relationship of an AE record (“Relationship to Study Treatment” on AE eCRF) is missing this AE will be considered “Probably Related” to the study treatment. If the AE severity is missing every effort should be made to acquire the information from the investigator. “Severe” will be assigned to a missing intensity for reporting purposes.

The general imputation rules of partial missing date for both AE and concomitant medication are detailed below:

Dates with missing the day of the year will adhere to the following conventions:

- The missing day of onset date will be set to:
 - First day of the month that the event occurred, if the onset YYYY-MM is after the YYYY-MM of the study treatment
 - The day of the study treatment, if the onset YYYY-MM is the same as YYYY-MM of the study treatment

- The date of informed consent, if the onset YYYY-MM is before the YYYY-MM of the study treatment.
- The missing day of end date will be set to:
 - The last day of the month of the occurrence. If the subject died in the same month, then set the imputed date as the death date.

Dates with missing both the day and month of the year will adhere to the following conventions:

- Missing day and month of onset date will be set to:
 - January 1 of the year of the onset, if the onset YYYY is after the YYYY of the study treatment
 - The date of the study treatment, if the onset YYYY is the same as YYYY of the study treatment
 - The date of informed consent, if the onset YYYY is before YYYY of the study treatment
- The missing date of end date will be set to:
 - December 31 of the year of occurrence. If the subject died in the same year, then set the imputed date as the death date.

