4.3.2.1. Average Daily Number of UUI Episodes

Average daily number of UUI episodes is calculated as the total number of UUI episodes recorded on the bladder diary days that fall within the visit window divided by the number of days the Bladder Diary is filled out. A UUI episode is defined as when a subject checked “Urge” to the question “select main reason for leakage” on the bladder diary eCRF. Subjects may have more than one bladder diary filled out on the same day and all the UUI episodes will be summed together. The denominator used for calculating the average number will only count the days in which there is a completed bladder diary day within the visit window.

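### With no post-baseline minimum of diary days in the SAP, one completed dry day is enough to count a subject as a 100% UUI responder

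*SAP*

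**What the plan says.** SAP 4.3.2.1 defines the daily UUI average with a denominator of completed days in the visit window: "The denominator used for calculating the average number will only count the days in which there is a completed bladder diary day". It sets no minimum. Micturitions, UI, urgency and nighttime voids (4.3.2.2 to 4.3.2.4 and 4.3.2.7) use the same kind of denominator. Protocol 9.4.1 also divides by the diary days present, with no minimum.

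On percent reduction in UUI, SAP 4.3.2.5 says "This is defined when both baseline and post-baseline average daily number of UUI episodes are non-missing" and then "For responder analyses, missing reduction from baseline will be considered non-responders for the visit in question". Section 4.3.2.8 repeats this for UI. Section 4.2.3 adds "If any missing data are present in diary data for any reasons, no imputation will be applied to derive responder" and makes subjects with missing assessments non-responders. It does not say whether a one- or two-day diary is a missing assessment.

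SAP 4.3.5 defines the diary baseline (the three "diary days collected during the screening and randomization period and closest to the treatment administration is considered baseline") and continues: "All 3 diary days are required for the change from baseline derivation". Later in that section: "If either the baseline or post-baseline value is missing, then change from baseline and percentage change from baseline will be set to missing".

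Protocol 8.2.1 and SAP Table 4 ask subjects to keep the diary on three consecutive days before each visit. The explicit three-day minimum in protocol 8.2.1 is an entry requirement.

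In the SAP's list of output tables, 100% UUI reduction (14.2.6.3) is marked for both topline and end of study. The 50% and 75% UUI tables (14.2.6.1 and 14.2.6.2) are marked for end of study only.

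**The concern.** A claim of complete dryness should need at least as much evidence as any other response. Under these rules it needs the least: the fewer days a subject who still leaks has recorded, the more likely all of them are dry. The scoring is also not monotone in the evidence. No diary is failure, one dry day is full success, and a second or third day can only take that success away.

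The 4.3.5 sentence adds an ambiguity. It names the change-from-baseline derivation, which uses a post-baseline value as well as a baseline one. A programmer who applies it after baseline gets different responder counts and different MMRM data from one who does not. At stake is how far the only UUI responder result in the topline set can be trusted, in a study whose interim results inform later planning.

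**Working it through.** **Plan's own figure.** The documents give no expected responder rate and no partial-diary rate, so there is nothing on this point to reproduce. (The stated 55% power does reproduce: noncentral t, 23 per group, df 44, gives 55.1%. It does not bear on this.)

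**Step 1: apply the rules to one subject.** Baseline 3 UUI/day (illustrative); one completed Week 12 day with 0 episodes. Average = 0/1 = 0. Reduction = −(0 − 3)/3 × 100 = 100%.

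| Completed Week 12 days, all dry | 4.3.5 sentence covers baseline only | 4.3.5 sentence also applied after baseline |
|---|---|---|
| 0 | Non-responder; no Week 12 value | Same |
| 1 or 2 | Responder at 50%, 75% and 100%; value enters MMRM | Change missing; non-responder at all three; no Week 12 value in MMRM |
| 3 | Responder at all three | Same |

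**Step 2: chance that a subject who still leaks is scored dry.** Assume episodes follow a Poisson process with rate λ per day. Then P(no episode in d days) = exp(−λd). Both λ and the Poisson form are assumptions.

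| λ per day | 1 day | 2 days | 3 days |
|---|---|---|---|
| 0.33 (one leak in three days) | 72% | 51% | 37% |
| 0.5 | 61% | 37% | 22% |
| 1 | 37% | 14% | 5% |

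If rates vary between subjects (gamma, mean 1.5/day, shape r, assumed), P = (1 + 1.5d/r)^(−r). For r = 0.6: 3.5^(−0.6) = 47% with one day and 8.5^(−0.6) = 28% with three. For r = 1: 1/2.5 = 40% and 1/5.5 = 18%. This mixture includes subjects whose rate is close to zero, so these shares are not all false.

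**Step 3: effect on an arm.** Let a share s of diaries have one day and the rest three.

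- Days counted as recorded: (1 − s)·exp(−3λ) + s·exp(−λ)
- Three days required: (1 − s)·exp(−3λ)
- Gap between the two: s·exp(−λ)

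With s = 10% (assumed) and 26 subjects per arm (SAP 1.2.4):

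| λ | As recorded | Three days required | If every diary had three days |
|---|---|---|---|
| 0.5 | 0.2008 + 0.0607 = 26.2% (6.8 of 26) | 20.1% (5.2 of 26) | 22.3% |
| 1 | 0.0448 + 0.0368 = 8.2% (2.1 of 26) | 4.5% (1.2 of 26) | 5.0% |

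Over s from 5% to 20% and λ from 0.5 to 2, the gap runs from 0.05 × 0.1353 = 0.7 points to 0.20 × 0.6065 = 12.1 points. One subject is 1/26 = 3.8 points.

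**Step 4: between arms.** The excess over complete diaries is s·[exp(−λ) − exp(−3λ)]. Arms with the same λ and the same s move together, so a spurious difference needs unequal s. If λ itself differs, equal s alters the difference slightly: at s = 10% the excess is 3.8 points for λ = 0.5 and 3.2 for λ = 1.

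**The case against.** Much can be said for the plan. Subjects must keep three consecutive days, are trained to do so, and have the instructions re-reviewed at visits, so one-day diaries may be rare. SAP 4.2.3 scores missing assessments as failures, and Table 4 describes the diary as three days, so a short diary could arguably be called missing. Even a full three-day diary scores 37% of subjects leaking at 0.33/day as dry, so part of the problem belongs to the instrument. The study has no formal hypothesis, its p-values are nominal, and topline UUI also includes the MMRM and by-visit summaries.

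These points limit the size and the stakes; they do not remove the defect. The three-day text governs collection, and a denominator that counts only completed days expects some diaries to be short. Section 4.2.3 never classes a partial diary as missing, while 4.3.2.5 asks only for a non-missing average.

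Three stronger readings are tempting and not supported. A reader might infer that poor diary compliance in general looks like cure: it does not, since a subject with no diary is a non-responder and only a partial diary that is also dry gains. A reader might infer bias towards URO-902: the documents give no reason for partial diaries to differ by arm in a double-blind, single-treatment trial. A reader might see a direct contradiction between 4.3.5 and 4.3.2.1: the 4.3.5 sentence directly follows the baseline definition and most naturally belongs to it, so the fault there is unclear scope.

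**Conclusion.** The point holds in a limited form. As written, one completed dry day after baseline counts as 100% UUI reduction, and the same logic applies to UI. For a subject still leaking at 0.33 to 0.5 episodes/day, one day instead of three raises the chance of being scored dry from 22–37% to 61–72%, on the Poisson assumption.

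The effect on the trial is unknown because the partial-diary rate is not given. With 10% one-day diaries and residual rates of 0.5 to 1 per day (all assumed), the 100% rate rises by 3.2 to 3.8 points over complete diaries, about one subject in 26. Every arm is inflated, and equally leaking arms are separated only if their partial-diary rates differ.

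The scope of the 4.3.5 sentence should be settled as well, since the two readings give different responder counts and MMRM data. That conclusion depends on none of the assumed rates.

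**What to change.** Amend the SAP before unblinding in three places.

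1. In 4.3.5, say that the three-day requirement covers the baseline diary only.
2. In 4.3.2.5 and 4.3.2.8, require three completed, episode-free diary days in the visit window for a 100% responder (UUI and UI). Otherwise the subject is a non-responder for that endpoint. This fits the plan's existing treatment of missing data as non-response.
3. State one post-baseline day-count rule and apply it to all diary endpoints: UUI, UI, micturitions, urgency and nighttime voids. The minimum for averages is the sponsor's choice. The documents supply no value, and for the MMRM it is a trade-off, since a noisier one-day average can still be used.

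The cost is wording, plus a few one- or two-day dry diaries that no longer count as 100% reduction. Depending on the minimum chosen for averages, such a subject could still be a 75% responder without being a 100% responder; the table footnote should say so. Interim analyses unblind some sponsor personnel, so a rule chosen after codes are seen would be open to the charge that the data drove it.

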5. DEMOGRAPHIC, OTHER BASELINE CHARACTERISTICS AND MEDICATION

5.1. Subject Disposition and Withdrawals

Subject disposition will be summarized for Screened population and by treatment group for the Randomized population separately. The summary for the screened population will include number of subjects who passed screening and who were screen failures and corresponding screen failure reasons.

For the disposition summary of the randomized population, the following categories will be presented; randomized, completed Week 24, completed Week 48 follow-up, withdrawn from study (and reason), received study treatment, did not receive any treatment, additional OAB treatment prescribed.

Reasons for exclusion from analysis population will also be summarized based on the populations defined in [Section 3.1](#).

The frequency and percentage of subjects with at least one major Protocol Deviation (PD), major PD by classification and reasons/category for PD will be summarized by treatment arm for the Randomized population.

Eligibility criteria, screen failures (including date and primary reason for failure), and informed consent (protocol version, informed consent version date and date signed) will be listed for all subjects screened.

A summary of randomized subjects by investigator name and site identification will be provided.

Randomization details will also be listed, including the date of randomization, randomization number and randomization strata.

